7.2.2 Hypoglycemia

Hypoglycemia will be regarded as an AE and recorded and documented on an AE form (and SAE form, if applicable).

Hypoglycemia is defined as a decline in plasma glucose to below 70 mg/dL (3.9 mmol/L). However, in the time period from initiation of the hypoglycemic clamp procedure (see Section 8.2.3.1) until 45 minutes after dosing, hypoglycemia is defined as a decline in plasma glucose to below 45 mg/dL (2.5 mmol/L).

During the dosing visit, prior to administration of the IMP, a plasma glucose value of <45 mg/dL (2.5 mmol/L) will be treated by an IV glucose solution. After administration of the IMP in the period from 8 minutes until 44 minutes after dosing, a plasma glucose value of <45 mg/dL (2.5 mmol/L) will be treated by an IV glucose solution, and if a plasma glucose value of \geq 70 mg/dL (3.9 mmol/L) is not achieved within the 45 minutes after IMP administration, IV glucose infusion will also be initiated.

If the subject experiences symptoms of hypoglycemia, a plasma glucose measurement should be taken in order to classify the event (please refer to Section 7.4.2 for additional details).

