9.7 Safety analyses

9.7.1 Adverse events

AEs will be coded using the latest available version of the MedDRA, the version of which will be provided in the clinical trial report. AE summary tables will include the number and percentage of subjects who experienced AEs summarized by system organ class and preferred term.

An overall summary table will be provided showing the number and percentage of subjects with any:

- TEAE
- Severe TEAE
- Serious TEAE
- Drug-related TEAE
- Drug-related severe TEAE
- Drug-related serious TEAE
- TEAE leading to withdrawal
- TEAE with outcome death
- AESI

Refer to Section [7.2.1](#) for the definition of TEAEs.

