7.2 Safety parameters

7.2.1 *Adverse events*

The investigator is responsible for the detection and documentation of events meeting the criteria and definition of an AE or serious adverse event (SAE), as provided in this protocol. During the trial, the investigator or center staff will be responsible for reporting AEs and SAEs, as detailed in this section of the protocol.

Based on the investigator's clinical judgment it will be determined whether an AE is related to treatment and of sufficient severity to require the subject's removal from treatment or from the trial. A subject may also voluntarily withdraw from treatment due to what he or she perceives as an intolerable AE. If either of these situations arises, the subject should be under medical supervision until symptoms cease or the condition becomes stable.

7.2.1.1 *Definitions*

Adverse event

An AE is any untoward medical occurrence in a trial subject given an IMP which does not necessarily have a causal relationship with the treatment. An AE can therefore be any unfavorable and/or unintended sign (for example, an abnormal laboratory finding), symptom, or disease temporally associated with the use of an IMP, whether or not considered related to the IMP.

In this trial, only treatment-emergent adverse events (TEAEs) will be collected and reported. TEAEs are events that occur from the first trial-related activity after the subject has signed the informed consent form until the end of the post-treatment follow-up period.

AEs include:

- A clinically significant worsening of a concomitant illness.
- A clinical laboratory abnormality which is clinically significant, i.e. any abnormality that suggests a disease and/or organ toxicity and is of a severity that requires active management. Active management includes active treatment or further investigations, for example change of medicine dose or more frequent follow-up due to the abnormality.
- Hypoglycemic episodes (see [Section 7.2.2](#)).
- Injection site reactions (see [Section 7.2.6](#)).

The following should not be recorded as AEs, if recorded at screening (on the Screening Form or eCRF):

- Pre-planned procedure, unless the condition for which the procedure was planned has worsened from the first trial related activity after the subject has signed the informed consent.
- Pre-existing conditions found as a result of screening procedures (pre-existing conditions should be reported as medical history or concomitant illness).

Serious adverse event

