7.2.1.2 Collection, recording and reporting of adverse events

All events meeting the definition of an AE must be collected and reported from the first trial related activity after the subject has signed the informed consent until the end of the post-treatment follow-up period. At each contact with the center (visit or telephone, excluding visits where the subject is not seeing the investigator or his/her staff [e.g. visits to the laboratory]) the subject must be asked about AEs. All AEs, either observed by the investigator or reported by the subject, must be recorded by the investigator and evaluated.

The investigator should record the diagnosis, if possible. If no diagnosis can be made the investigator should record each sign and symptom as individual AEs.

One single Adverse Event Form must be used per AE from start to resolution. For SAEs, the Serious Adverse Event form must also be completed. For AESIs, the AESI form must also be completed.

AE information should include the following:

- Date and time of onset and resolution
- Date and time of investigator's first information on the (S)AE
- Seriousness
- Severity
- Causal relationship with IMP
- Interruption or withdrawal of treatment during IMP administration and other measures taken
- Outcome.

All AEs are coded; details are described in the trial-specific Data Management Plan.

If an event classifies as a AESI, the investigator must tick the AESI box on the AE form and complete the AESI form. The AESI form will capture if the event was associated with any signs or symptoms and capture the highest/lowest blood pressure and pulse measured during the event. The investigator must report all AESIs to the sponsor's responsible pharmacovigilance unit (Safety CRO; see the list of trial personnel in [Section 12.1](#)) immediately (within 24 hours) after obtaining knowledge about the event.

The investigator must report initial information electronically (e.g. in PDF format) on all SAEs to the sponsor's responsible pharmacovigilance unit (Safety CRO; see the list of trial personnel in [Section 12.1](#)) immediately (within 24 hours) after obtaining knowledge about the event. The Safety CRO will inform the medical monitor and the sponsor about the reported SAEs.

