7.2.2 Hypoglycemia

Hypoglycemia will be regarded as an AE and recorded and documented on an AE form (and SAE form, if applicable).

Hypoglycemia is defined as a decline in plasma glucose to below 70 mg/dL (3.9 mmol/L). However, in the time period from initiation of the hypoglycemic clamp procedure (see [Section 8.2.3.1](#)) until 45 minutes after dosing, hypoglycemia is defined as a decline in plasma glucose to below 45 mg/dL (2.5 mmol/L).

During the dosing visit, prior to administration of the IMP, a plasma glucose value of <45 mg/dL (2.5 mmol/L) will be treated by an IV glucose solution. After administration of the IMP in the period from 8 minutes until 44 minutes after dosing, a plasma glucose value of <45 mg/dL (2.5 mmol/L) will be treated by an IV glucose solution, and if a plasma glucose value of \geq 70 mg/dL (3.9 mmol/L) is not achieved within the 45 minutes after IMP administration, IV glucose infusion will also be initiated.

If the subject experiences symptoms of hypoglycemia, a plasma glucose measurement should be taken in order to classify the event (please refer to [Section 7.4.2](#) for additional details).

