7.2 Safety parameters

7.2.1 *Adverse events*

The investigator is responsible for the detection and documentation of events meeting the criteria and definition of an AE or serious adverse event (SAE), as provided in this protocol. During the trial, the investigator or center staff will be responsible for reporting AEs and SAEs, as detailed in this section of the protocol.

Based on the investigator's clinical judgment it will be determined whether an AE is related to treatment and of sufficient severity to require the subject's removal from treatment or from the trial. A subject may also voluntarily withdraw from treatment due to what he or she perceives as an intolerable AE. If either of these situations arises, the subject should be under medical supervision until symptoms cease or the condition becomes stable.

7.2.1.1 *Definitions*

Adverse event

An AE is any untoward medical occurrence in a trial subject given an IMP which does not necessarily have a causal relationship with the treatment. An AE can therefore be any unfavorable and/or unintended sign (for example, an abnormal laboratory finding), symptom, or disease temporally associated with the use of an IMP, whether or not considered related to the IMP.

In this trial, only treatment-emergent adverse events (TEAEs) will be collected and reported. TEAEs are events that occur from the first trial-related activity after the subject has signed the informed consent form until the end of the post-treatment follow-up period.

AEs include:

- A clinically significant worsening of a concomitant illness.
- A clinical laboratory abnormality which is clinically significant, i.e. any abnormality that suggests a disease and/or organ toxicity and is of a severity that requires active management. Active management includes active treatment or further investigations, for example change of medicine dose or more frequent follow-up due to the abnormality.
- Hypoglycemic episodes (see Section 7.2.2).
- Injection site reactions (see Section 7.2.6).

The following should not be recorded as AEs, if recorded at screening (on the Screening Form or eCRF):

- Pre-planned procedure, unless the condition for which the procedure was planned has worsened from the first trial related activity after the subject has signed the informed consent.
- Pre-existing conditions found as a result of screening procedures (pre-existing conditions should be reported as medical history or concomitant illness).

Serious adverse event

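### TEAEs are counted from informed consent rather than from injection, so pre-dose events of dosed subjects are labelled treatment-emergent and can attenuate several descriptive safety contrasts

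*Protocol*

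**What the plan says.** Section 7.2.1.1 first limits what is gathered: "In this trial, only treatment-emergent adverse events (TEAEs) will be collected and reported". It then sets the start of the window: "TEAEs are events that occur from the first trial-related activity after the subject has signed the informed consent form". The window closes at the end of post-treatment follow-up. Section 7.2.1.2 gives AE collection the same start: "All events meeting the definition of an AE must be collected and reported from the first trial related activity".

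Section 7.2.2 makes hypoglycemia an AE. The general threshold is 70 mg/dL, with a lower one around the clamp: "However, in the time period from initiation of the hypoglycemic clamp procedure" until 45 minutes after dosing, "hypoglycemia is defined as a decline in plasma glucose to below 45 mg/dL (2.5 mmol/L"). The same section foresees such values before injection and states how they are handled: "prior to administration of the IMP, a plasma glucose value of" less than 45 mg/dL is treated with IV glucose.

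Section 9.7.1 announces the safety tables: "An overall summary table will be provided showing the number and percentage of subjects with any" of nine categories. Seven of these are some kind of TEAE, one is TEAE with outcome death, and one is AESI. For the meaning of TEAE it refers back to Section 7.2.1.

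The file holds three versions of the protocol. The two complete ones carry identical wording in Section 7.2.1.1. The version placed first is shown only from a point after that section, but its Section 9.7.1 still refers to Section 7.2.1.

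**The concern.** A treatment-emergent label should separate what happened after exposure from what happened before it. Here it separates nothing, because every collected AE is a TEAE by definition. The trial gives one injection at a recorded time. Before it come up to 30 days of screening, a change of insulin regimen, an overnight stay and an insulin infusion intended to lower glucose. An event in that period cannot be caused by the injection, yet it enters the TEAE percentages of the arm to which the subject was randomized.

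The affected terms include ones that matter for this drug. Section 2.1.3.2 names nausea as the most frequent systemic AE of dasiglucagon, and Section 2.1.1 lists nausea among the symptoms of hypoglycemia. Under Section 7.2.1.2, symptoms without a diagnosis are recorded one by one. Nausea during the infusion could therefore fall under the same preferred term as the drug's known effect. At stake is a fair descriptive picture of how often events follow each treatment.

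**Working it through.** **No stated figure to reproduce.** The protocol gives no AE or TEAE rate. Its only power figure is the 90% for recovery within 20 minutes (Section 9.1: 78 versus 39 subjects, 80% versus 50%, two-sided 5%). That figure reproduces (91.1% with pooled variance, 90.3% unpooled, 88.9% with Fisher's exact test), and the TEAE definition does not enter it.

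**Which events fall before dosing.**
- Section 8.2.1 places screening 3 to 30 days before the dosing visit. Section 10.10 gives at most 30 + 33 = 63 days per subject, so up to 30/63 = 48% of participation can precede the injection.
- Table 3 schedules AE assessment at screening.
- Sections 7.2.2 and 8.2.3.1 anticipate glucose below 45 mg/dL before dosing.
- The safety analysis set (Section 9.2.1) contains dosed subjects only. Events in screen failures stay out of the tables; pre-dose events of dosed subjects come in.

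**Which outputs are exposed.**

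| Output in Section 9.7.1 | Effect |
|---|---|
| Any, severe, serious TEAE | Exposed |
| TEAE leading to withdrawal, TEAE with outcome death | Exposed, but only if withdrawal or death follows dosing |
| Three drug-related rows | Largely protected by the causality rating |
| AESI | Unaffected: both bullets of its definition are post-dose |
| Preferred terms possible before dosing (e.g. hypoglycemia, nausea) | Exposed |
| Injection-site reactions | Unaffected: cannot precede injection |

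**Size of the dilution.** Let p be the post-dose incidence in an arm and q the probability of at least one pre-dose event. Assume q is equal across arms and independent of post-dose events. The tabulated incidence is

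P = 1 − (1 − p)(1 − q),

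so the risk difference becomes (1 − q)(p₁ − p₂) and the risk ratio moves toward 1.

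Illustration with p₁ = 60% and p₂ = 20%. Both rates and all values of q are assumptions; none is in the protocol.

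| q | Tabulated rates | Risk difference (points) | Risk ratio |
|---|---|---|---|
| 0% | 60 vs 20 | 40 | 3.0 |
| 2% | 60.8 vs 21.6 | 39.2 | 2.8 |
| 5% | 62 vs 24 | 38 | 2.6 |
| 10% | 64 vs 28 | 36 | 2.3 |
| 20% | 68 vs 36 | 32 | 1.9 |
| 30% | 72 vs 44 | 28 | 1.6 |

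For example, at q = 20%: 1 − 0.4 × 0.8 = 0.68 and 1 − 0.8 × 0.8 = 0.36, so the difference is 0.32 and the ratio 1.9.

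With lower assumed post-dose rates of 30% versus 10%, the starting ratio is again 3.00. It falls to 1.95, 1.57 and 1.38 at q = 10%, 20% and 30%.

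**On the assumptions.** Randomization makes equal q reasonable in expectation, because treatment has not yet been given. Independence is less secure: if the same subjects tend to have events in both periods, pre-dose events add fewer subjects to each arm and the factor (1 − q) is no longer exact.

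**The case against.** Several points on the other side stand.

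- **Reach.** A reader might infer that every safety row is diluted. The documents do not support that: the AESI row is post-dose by definition, a pre-injection event would be expected to be rated unrelated to trial product, and injection-site reactions cannot occur early.
- **Consequence.** A reader might infer that drug effects are hidden or a test is weakened. No test of AE incidence is planned. Onset date and time are recorded and eCRF data are listed, so pre- and post-dose events remain separable.
- **Sample size.** Section 9.1 ties the 78 dasiglucagon subjects to safety-database needs. It is tempting to say the definition undermines that purpose, but 78 is a count of exposed subjects and the TEAE start does not change it.
- **Version.** The wording of Section 7.2.1.1 in the version placed first is not visible. The versions differ elsewhere, for example on insulin wash-out, so unchanged wording is an inference, though the pointer in its Section 9.7.1 remains.
- **Size.** The values of q are not sourced; at 2% the effect is slight.

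Two further arguments carry less weight. The SAP may refine details, but this is a rule the protocol states and its tables invoke, not a detail left open. One could also say that pre-dose events are not AEs at all, since Section 7.2.1.1 holds that "An AE is any untoward medical occurrence in a trial subject given an IMP". Taken literally, that conflicts with the window in the same section, with AE assessment at screening in Table 3, and with Section 7.2.2, which applies its AE definition from the start of the clamp. It adds an inconsistency rather than a repair.

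**Conclusion.** The point holds as a defect of definition with limited reach. In the two complete versions, TEAE and AE are the same set, and nothing shown in any version restricts TEAEs to onset or worsening after injection. Five summary rows and the preferred terms that can arise before dosing are mislabelled, and their between-arm contrast can be attenuated. Given equal and independent pre-dose risk, the direction is certain for any q above zero. The amount ranges from trivial (risk ratio 3.0 to 2.8 at q = 2%) to substantial (3.0 to 1.6 at q = 30%) under the assumed 60% versus 20%. The documents cannot place q within or outside that range. No confirmatory result, error rate or sample-size figure is affected.

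**What to change.** Keep AE collection from consent. In Section 7.2.1.1, define a TEAE as an AE with onset, or worsening of an existing event, at or after the IMP injection (t = 0) until the end of follow-up. In Section 9.7.1, tabulate AEs with onset before injection separately as non-treatment-emergent. Remove the statement that only TEAEs are collected, and reword the AE definition so that it agrees with collection from consent. Check that the same text appears in Section 7.2.1.1 of the version placed first.

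The cost is one definition, one derived flag in the AE dataset and one extra table. AE onset date and time (Section 7.2.1.2) and the time of IMP administration (Section 8.2.3.1) are already recorded, so no new data are needed and clinical procedures do not change.

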7.2.1.2 Collection, recording and reporting of adverse events

All events meeting the definition of an AE must be collected and reported from the first trial related activity after the subject has signed the informed consent until the end of the post-treatment follow-up period. At each contact with the center (visit or telephone, excluding visits where the subject is not seeing the investigator or his/her staff [e.g. visits to the laboratory]) the subject must be asked about AEs. All AEs, either observed by the investigator or reported by the subject, must be recorded by the investigator and evaluated.

The investigator should record the diagnosis, if possible. If no diagnosis can be made the investigator should record each sign and symptom as individual AEs.

One single Adverse Event Form must be used per AE from start to resolution. For SAEs, the Serious Adverse Event form must also be completed. For AESIs, the AESI form must also be completed.

AE information should include the following:

- Date and time of onset and resolution
- Date and time of investigator's first information on the (S)AE
- Seriousness
- Severity
- Causal relationship with IMP
- Interruption or withdrawal of treatment during IMP administration and other measures taken
- Outcome.

All AEs are coded; details are described in the trial-specific Data Management Plan.

If an event classifies as a AESI, the investigator must tick the AESI box on the AE form and complete the AESI form. The AESI form will capture if the event was associated with any signs or symptoms and capture the highest/lowest blood pressure and pulse measured during the event. The investigator must report all AESIs to the sponsor's responsible pharmacovigilance unit (Safety CRO; see the list of trial personnel in [Section 12.1](#)) immediately (within 24 hours) after obtaining knowledge about the event.

The investigator must report initial information electronically (e.g. in PDF format) on all SAEs to the sponsor's responsible pharmacovigilance unit (Safety CRO; see the list of trial personnel in [Section 12.1](#)) immediately (within 24 hours) after obtaining knowledge about the event. The Safety CRO will inform the medical monitor and the sponsor about the reported SAEs.

It is the responsibility of the Safety CRO to report all SUSARs (see [Section 7.2.1.1](#)) that occur in this trial to the Competent Authorities and Institutional Review Boards (IRBs)/Independent Ethics Committees (IECs) in accordance with the local requirements in force and ICH guideline for GCP. The trial monitor must be informed accordingly.

7.2.1.3 Follow-up of adverse events

All AEs that are ongoing at the end of the subject's participation in the trial will be followed-up until the event is resolved or reaches a satisfactory outcome as deemed by the investigator or until the last visit of the last subject enrolled in the trial, whichever occurs first.

Follow-up actions for all SAEs will be performed according to appropriate clinical care practices and may depend on the nature of the event. These will be determined after internal review and/or sponsor review.

The follow-up information should only include new (updated and/or additional) information that reflects the situation at the time of the investigator's signature.

Follow-up information on (S)AEs will be updated using the (S)AE form. If a non-serious event becomes serious during the follow-up the AE form and SAE form have to be used and reporting timelines follow those of an SAE.

The investigator must forward follow-up information on SAEs and if previously non-serious AEs become SAEs to the Safety CRO immediately (within 24 hours) after obtaining knowledge about the new information.

The sponsor and/or CROs acting on behalf of the sponsor can upgrade a non-serious AE to an SAE. In these situations the investigator will be informed and asked to fill out an SAE form and forward to the Safety CRO immediately (within 24 hours).

7.2.1.4 Clinical laboratory abnormalities and other abnormal assessments as adverse events or serious adverse events

Abnormal laboratory findings (e.g. biochemistry, hematology, urinalysis) or other abnormal assessments (e.g. vital signs) that are judged by the investigator as **clinically significant** will be recorded as AEs or SAEs if they meet the definition of an AE or SAE. Clinically significant abnormal laboratory findings or other abnormal assessments that are detected during the trial or are present at baseline and significantly worsen following the start of the trial will be reported as AEs or SAEs. However, clinically significant abnormal laboratory findings or other abnormal assessments that are associated with the disease being studied, unless judged by the investigator as more severe than expected for the subject's condition, or that are present or detected at the start of the trial and do not worsen, will not be reported as AEs or SAEs.

The investigator will exercise his or her medical and scientific judgment in deciding whether an abnormal laboratory finding or other abnormal assessment is clinically significant.

